## **1. OBJECTIVES**

## 1.1 Study Design

This is a single arm, open-label phase II study evaluating the safety and efficacy of the combination of the third-generation EGFR inhibitor EGF816 with the first-generation EGFR inhibitor gefitinib in the treatment of TKI-naïve *EGFR*-mutant non-small cell lung cancer. The study will have a Simon two-stage design with eleven patients enrolled in the first stage and a plan to enroll a total of 36 patients (25 patients in the second stage) if at least seven patients remain progression-free at nine months in the first stage. The first six patients enrolled in the study will constitute a safety run-in evaluating the safety of the combination of EGF816 at the recommended phase II dose of 150mg QD and gefitinib at a standard dose of 250mg QD. If unexpected toxicities are observed among the first six patients, expansion cohorts will be added to explore different doses and/or schedules of the combination.

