# 5. TREATMENT PLAN

## 5.1 Treatment Regimen

All patients will receive combination therapy with EGF816 and gefitinib in an open-label fashion. A treatment cycle will be defined as 28 days. After completing 1 year of study treatment, visits will occur every 6 weeks.

The first six patients enrolled in the study will constitute a safety run-in; if severe unexpected toxicities are observed during cycle 1 among these six patients, further expansion cohorts at lower dose levels will be explored. Severe unexpected toxicities will be defined as any grade 3 or higher adverse event assessed to be treatment-related by the treating physician occurring in > 1/6 patients during the safety run-in. Rash will be excluded as grade 3 rash during the 1st cycle has occured with each drug individually and is typically responsive to dose hold. If >1 patient has a grade 3 or higher treatment-related adverse event during cycle 1 of treatment, we will de-escalate treatment to gefitinib 250 mg QD and EGF816 100 mg QD.

EGF816 will be supplied by Novartis to the investigational drug pharmacy at all participating sites. Gefitinib will be supplied directly to the patient through prescription as a commercial product. As stated in the eligibility criteria, only patients with insurance approval to obtain gefitinib or who agree to self-pay for gefitinib will be able to participate in this study. Upon signing of the study ICF and confirmation of eligibility, participants will be prescribed a 30-day (one 28-day cycle; with two additional pills in case of lost, dropped pills) supply of gefitinib. C1D1 will begin only once the supply of gefitinib is in the patient's possession.

All patients will receive gefitinib 250 mg orally once daily and EGF816 100 mg orally once daily without interruption, unless an interruption is required to manage treatment-related toxicity (as outlined in Tables 6-1 and 6-2). Patients will be monitored at the start of each 28-day treatment cycle. Treatment will be administered on an outpatient basis. The participant will be requested to maintain a medication diary of each dose of medication. The medication diary will be returned to clinic staff at the end of each cycle.

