#### 5.3 Agent Administration

#### 5.3.1 EGF816

Investigational Product: EGF816 Pharmaceutical Form: Tablets Source: Novartis Procurement: Provided via sponsor, dispensed from research pharmacy. Unit Strength: 150mg tablets Daily Dose: 100 mg once daily Duration of Use: Continuous daily dosing without interruption Administration Route: Oral (swallowed) Schedule: Once daily, with or without food

Missed Doses/Vomited Doses: If a patient inadvertently does not take the EGF816 dose at their usual time, he or she may take the dose up to 6 hours later; in other words, they may continue as long as it is at least 6 hours before the next dose of gefitinib is due to be taken. The daily treatment schedule will be resumed the next day with the patient taking the scheduled dose at the usual time. If an entire daily dose is skipped, the patient should resume treatment the following day with their regular dose. No "make-up dose" or increased dosing should occur. If a dose is vomited within 1 hour of administration, medications to control nausea and vomiting should be used, and the dose can be repeated. Patients should report all vomited, missed or delayed doses to the study staff and will be provided with a medication diary which should be turned in at every visit (see appendix 5.)

Tablets should be swallowed whole and not chewed or opened. Patients should be instructed to take their dose of each drug at approximately the same time of day. Drugs should be separated by approximately 12 hours (e.g, gefitinib taken in the morning and EGF816 in the evening.) The time of drug administration should be recorded by the patient in the study-provided drug diary. On days when blood for PK samples need to be collected in clinic, the patient should hold their morning gefitinib until arrival, and take the dose in the clinic after clearance to do so from the care team.

Grapefruit or grapefruit juice, seville orange (and juice), pummelos, star citrus fruits and hybrids of these mentioned fruits should be avoided during study treatment.

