## 6. DOSING DELAYS/DOSE MODIFICATIONS

Dose delays and modifications will be made as indicated in the following table(s). The descriptions and grading scales found in the revised NCI Common Terminology Criteria for Adverse Events (CTCAE) version 4.0 will be utilized for dose delays and dose modifications. A copy of the CTCAE version 4.0 can be downloaded from the CTEP website http://ctep.cancer.gov/protocolDevelopment/electronic\_applications/ctc.htm.

Dose delays and modifications will be made as indicated in the following table(s). The descriptions and grading scales found in the revised NCI Common Terminology Criteria for Adverse Events (CTCAE) version 4.0 will be utilized for dose delays and dose modifications. A copy of the CTCAE version 4.0 can be downloaded from the CTEP website http://ctep.cancer.gov/protocolDevelopment/electronic applications/ctc.htm.

EGF816 and gefitinib are both EGFR tyrosine kinase inhibitors and have both overlapping and distinct toxicities. Guidelines for the management of potentially drug-related toxicities, including dose interruptions and dose reductions of each drug, are provided in section 6.1.

When possible, toxicities should be managed with appropriate medical treatment (including antiemetics, anti-diarrheals, etc.) Other contributing factors, including concomitant medications which may be contributing to the toxicity, should be identified and discontinued or dose reduced if appropriate. The following sections provide guidelines for dose modification and dose interruption (i.e., interruption and re-initiation criteria for EGF816 and gefitinib treatment). All dose modifications should be based on the worst preceding toxicity (CTCAE version 4.0). If, due to study drug related toxicity, a patient requires a dose interruption of >28 days from the intended day of the next scheduled dose, then the patient must be discontinued from the study treatment. Each patient is allowed no more than two dose reductions of each study drug. In addition, a patient must discontinue treatment with EGF816 and gefitinib if, after treatment is resumed at a lower dose, the toxicity recurs with the same or worse severity.

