## 6.1 Conditions requiring dose modification:

The dose modification levels for EGF816 are as follows:

Dose Level	EGF816 Dose
0	100 mg once daily
-1	75 mg once daily
-2	50 mg once daily

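### The EGF816 run-in dose is 150 mg in section 1.1 but 100 mg elsewhere, which is also the de-escalation target, and the dose-reduction column in 13.7 does not match the >1-of-6 rule

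*Combined protocol and SAP*

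**What the plan says.** Section 1.1 describes a six-patient safety run-in of "EGF816 at the recommended phase II dose of 150mg QD and gefitinib at a standard dose of 250mg QD". If unexpected toxicity appears, it leaves other doses or schedules to be explored.

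Section 5.1 gives a different dose: "All patients will receive gefitinib 250 mg orally once daily and EGF816 100 mg orally once daily without interruption". Section 5.3.1 repeats 100 mg as the daily dose, and Table 6-1 sets level 0 at 100 mg, with 75 mg and 50 mg as levels -1 and -2.

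For the run-in itself, 5.1 says first that "further expansion cohorts at lower dose levels will be explored". It then fixes the trigger at more than one of six patients with a related grade 3 or higher event in cycle 1, not counting rash, and names the action: "we will de-escalate treatment to gefitinib 250 mg QD and EGF816 100 mg QD". Section 13.7 repeats the trigger, refers back to 5.1 for the step, and adds six patients at a lower dose without giving it in milligrams. It then tabulates, by true toxicity rate, the chance of reducing the starting dose and the chance of stopping the trial.

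The product entry in 5.3.1 reads "Unit Strength: 150mg tablets Daily Dose: 100 mg once daily", and also "Tablets should be swallowed whole and not chewed or opened".

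**The concern.** A de-escalation rule needs a starting dose and a lower dose to move to. Here the dose named for everyone and the dose named as the step down are the same regimen, while the study design section gives a higher one. A site, a pharmacy or a reader of the results has to guess which dose the run-in tested. If 100 mg is the start, the rule can fire with no cohort dose below it fixed in advance, so the next dose would be chosen after the toxicity is seen. If 100 mg is the result of a step down, a reader cannot tell from the text that the run-in patients had a different dose from the rest.

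The table in 13.7 is the plan's only statement of how the run-in rule behaves. If its columns do not correspond to the written trigger, the rule looks far more ready to lower the dose than it is.

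**Working it through.** **Dose statements side by side**

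| Place | EGF816 daily dose |
|---|---|
| 1.1, run-in | 150 mg |
| 5.1, all patients | 100 mg |
| 5.1, run-in de-escalation target | 100 mg |
| 5.3.1, daily dose | 100 mg |
| Table 6-1, level 0 | 100 mg |
| 13.7, second run-in cohort | a lower dose, no value |

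Reading A: 100 mg is the start. The named step is 100 to 100 mg, which is no reduction, and the second cohort in 13.7 has no stated dose.

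Reading B: the start was 150 mg and 100 mg followed a de-escalation. The step is 150 to 100 mg, a reduction of 50 mg, and the rule works. But the 100 mg statement for all patients is then wrong for the run-in, 1.1 does not record the change, and Table 6-1 has no level for a patient on 150 mg.

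The 75 and 50 mg levels do not settle this. Section 6 frames them as individual reductions ("Each patient is allowed no more than two dose reductions of each study drug"), and the run-in rule does not refer to them.

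Tablets: whole 150 mg tablets give 150, 300 mg and so on. None of 100, 75 or 50 mg can be made, whichever start was meant.

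**The table in 13.7**

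Inputs: n = 6 per cohort and trigger X > 1 (5.1 and 13.7); true rates p as printed in 13.7. X is binomial(6, p).

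- At least one event: P(X≥1) = 1 − (1−p)^6
- The written rule: P(X>1) = 1 − (1−p)^6 − 6p(1−p)^5

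Example at p = 0.20: (0.8)^6 = 0.2621 and 6 × 0.2 × (0.8)^5 = 0.3932. So P(X≥1) = 0.7379 and P(X>1) = 0.3446.

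| p | Printed: reduce dose | P(X≥1) | P(X>1), written rule | Printed: stop trial | Printed reduction minus P(X>1) |
|---|---|---|---|---|---|
| 0.05 | 0.265 | 0.2649 | 0.0328 | 0.033 | 0.232 |
| 0.10 | 0.468 | 0.4686 | 0.1143 | 0.114 | 0.354 |
| 0.20 | 0.738 | 0.7379 | 0.3446 | 0.345 | 0.393 |
| 0.30 | 0.883 | 0.8824 | 0.5798 | 0.580 | 0.303 |
| 0.40 | 0.954 | 0.9533 | 0.7667 | 0.767 | 0.187 |
| 0.50 | 0.985 | 0.9844 | 0.8906 | 0.890 | 0.094 |

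Both printed columns are reproduced to within 0.001. The dose-reduction column follows a trigger of at least one of six. The stopping column is the written trigger applied to a single cohort.

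The stopping column is therefore right only as a probability conditional on having reached the lower-dose cohort, with the same trigger used there. Stopping as seen from the start requires the rule to fire twice. If p is the same in both cohorts, that is P(X>1)²: 0.001, 0.013, 0.119, 0.336, 0.588 and 0.793.

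**The case against.** The strongest reply is that reading B is the natural one. A step down to 100 mg makes sense only from above 100 mg, 1.1 states 150 mg outright, and the listed tablet is 150 mg. A page header in section 6.1.3 carries a January 2019 version date, so 100 mg text added after the run-in beside unrevised wording is plausible. This carries weight, and the documents do not favour reading A. But the text read does not say that the run-in finished, that the dose was lowered, or that 150 mg applied only to early patients. The schema diagram and part of section 2.2.2 were not available, so an explanation there cannot be excluded.

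A reader might infer that the run-in had no effective safety check. The documents do not support that. Table 6-1 defines levels below 100 mg, individual reductions apply throughout, 1.1 allows other doses or schedules, and section 12.2 provides for safety committee review of toxicity. What is missing, on reading A only, is a cohort dose fixed in advance.

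A reader might also infer that the table misled the safety committee or governed conduct. No section says the committee uses it, and the trigger of more than one in six is the same in 5.1 and 13.7. The tablet entry may be clerical: section 2.2.2 reports 75 and 100 mg among doses given as capsules or tablets. It is still wrong as written.

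**Conclusion.** The point stands as an internal inconsistency that should be corrected, not as a design fault that undermines the trial. Two things are wrong as written.

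First, the EGF816 dose conflicts between 1.1 and 5.1, 5.3.1 and Table 6-1. The consequence depends on a fact the text does not give. On reading A, the rule fires with probability 0.033 to 0.891 over true rates of 0.05 to 0.50 and names no lower cohort dose. On reading B, the rule lowers the dose as intended and the fault is inaccurate text.

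Second, on either reading the dose-reduction column in 13.7 overstates the written rule by 0.09 to 0.39, most at a 20% rate (0.738 against 0.345).

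The probabilities assume independent patients with a common rate of qualifying events; rash does not qualify under 5.1. The unconditional stopping figures also assume the same rate at both doses, which is conservative if the lower dose is less toxic.

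It would be wrong to infer an effect on the efficacy test. The Simon rule (11 then 25 patients, continue at 7, reject at 23) gives a one-sided error of 0.048 at 50% and power of 0.811 at 73%, in line with the plan, and involves neither the dose nor the run-in table. If the run-in is complete, the corrections concern text and table only.

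**What to change.** State one starting dose and one strictly lower run-in target, the same in 1.1, 5.1, 5.3.1, Table 6-1 and 13.7.

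- If the start was 150 mg: record the step to 100 mg in 1.1 and 5.1, and limit the all-patients statement to those enrolled after it.
- If the start is 100 mg: correct 1.1 and tie the run-in rule to Table 6-1 level -1, 75 mg. Section 2.2.2 reports seven patients at that dose, and 2.2.1 describes it as apparently efficacious.

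In 5.3.1, list a tablet strength that can deliver 100, 75 and 50 mg.

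In 13.7, replace the dose-reduction column with 0.033, 0.114, 0.345, 0.580, 0.767 and 0.891, or change the trigger to at least one of six in 5.1 and 13.7 if that was intended. If the written trigger is kept, the two columns will then agree apart from rounding in the last row. The stopping column should therefore be labelled as conditional on reaching the lower-dose cohort, with the same trigger stated as its criterion. If an unconditional figure is preferred, use 0.001, 0.013, 0.119, 0.336, 0.588 and 0.793, and state that the same rate is assumed in both cohorts.

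The cost is amendment wording in five places, one tablet entry, one table column and one column label. Sample size, cut-offs and follow-up do not change.

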## **1.2** Primary Objectives

The primary objective of the study is to evaluate the efficacy of EGF816 in combination with gefitinib in the treatment of TKI-naïve EGFR-mutant NSCLC. Efficacy will be measured as proportion that are progression-free at 39 weeks.

## **1.3** Secondary Objectives

The secondary objectives of the study will include:

- To describe the median progression free and overall survival of patients treated with EGF816 and gefitinib.
- To evaluate the safety and tolerability of the EGF816/gefitinib combination.

## 1.4 Exploratory Objectives

- To characterize the pharmacokinetic interactions between gefitinib and EGF816.
- To evaluate resistance mechanisms to EGF816 and gefitinib.
- To characterize the molecular response to treatment in on-treatment tumor biopsies and in circulating tumor DNA.

## **2.** BACKGROUND

## 2.1 Study Disease(s)

Non small cell lung cancer (NSCLC) is a heterogeneous entity which affects over 220,000 people in the US each year, and is the leading cause of cancer-related mortality in the world. Over half of NSCLC patients have advanced or metastatic disease at presentation. Unfortunately, metastatic disease is not curable, and current chemotherapy offers only modest improvements in survival. Recently, genetic alterations leading to an "oncogene-addicted" biology have been shown to occur in a subset of NSCLC patients and confer sensitivity to specific tyrosine kinase inhibitors  $(TKI's.)^3$ These biologically targeted agents have had a significant impact on the survival of patients carrying such genetic alterations, but their efficacy is limited and the discovery of novel ways to prolong the disease course remains a top research priority.

The epidermal growth factor receptor (EGFR) receptor signaling pathway plays a central role in the neoplastic transformation of NSCLC and promotes cancer cell survival, metastasis and angiogenesis. Somatic mutations in the EGFR gene in NSCLC tumors have been well-described. EGFR mutations are present in about 10% of unselected US patients with NSCLC, but in up to 50% of never-smoking NSCLC patients. Although a variety of mutations within EGFR have been described, the most common of these mutations include exon 19 deletion and the L858R mutation in exon 21, both of which sensitize NSCLC tumors to treatment with EGFR TKIs such as gefitinib and erlotinib. Erlotinib and gefitinib have now been shown to improve both response rates and progression-free survival in patients with EGFR-mutant NSCLC in multiple randomized trials.

Although remarkable response rates are seen in patients with EGFR mutations that are treated with EGFR TKIs (~ 80%), the responses are of limited duration because eventually patients develop "acquired resistance". Several resistance mechanisms have been identified, the most common being a secondary mutation at the threonine gatekeeper residue at position 790, T790M, which develops in up to 50% of NSCLC patients harboring a primary EGFR mutation treated with first generation EGFR TKIs.

Third generation EGFR inhibitors targeting T790M and activating EGFR mutations with relative sparing of wild-type EGFR have now been developed. One such drug, osimertinib, received FDA approval based on objective response rate of ~60% among patients with T790M-mediated acquired resistance to initial EGFR inhibitor. Several other third-generation EGFR inhibitors, including EGF816, are in clinical development and have shown equally promising activity. Unfortunately, the activity of these new drugs is also limited by the eventual development of acquired resistance, with current PFS estimates of about 9-13 months on osimertinib and other third-generation EGFR inhibitors.

Recent reports show that resistance to osimertinib, olmutinib and rociletinib can be mediated by the development of a new tertiary resistance mutation, C797S, which occurs at the site of covalent binding of all irreversible EGFR inhibitors, and has previously been identified as a putative resistance mechanism to this class of drugs in in vitro models. Other resistance mechanisms, including MET amplification, Her2 amplification, BRAF mutations and SCLC transformation have also been identified in individual cases treated with third-generation EGFR inhibitors, and there is growing evidence that resistance to these novel agents may develop in the setting of increasing molecular heterogeneity and that multiple resistance mechanisms can coexist in cancers progressing on third-generation EGFR TKIs.

Since cancers treated with sequential single-agent EGFR inhibitors have repeatedly demonstrated the ability to overcome such drugs through eventual development of resistance mechanisms including T790M and C797S, we hypothesize that using combinations of a first- and third-generation EGFR inhibitor in the first-line setting may delay the development of acquired resistance as neither resistance mutation alone would be sufficient to overcome the combination.

# 2.2 EGF816

## 2.2.1 Overview and non-clinical experience

EGF816 is a targeted covalent epidermal growth factor receptor (EGFR) inhibitor that selectively inhibits activating and resistance mutants (L858R, Exon 19 deletion mutation(s) of EGFR (ex19del), and T790M) while sparing wild type (WT) EGFR. First and second generation inhibitors of EGFR, which target activating mutations as well as WT EGFR, have been validated as therapeutic agents in specific scenarios; however, the narrow therapeutic window of these EGFR inhibitors, by inhibiting both mutant EGFR within the tumor and WT EGFR within normal tissues, significantly limits the maximum potential of this class of drugs. By sparing WT EGFR, while inhibiting mutant EGFR, EGF816 has the potential to improve upon the first and second generation EGFR inhibitors. Additionally, by inhibiting EGFR T790M, EGF816 offers a therapeutic option for patients harboring that mutation. EGF816 demonstrated efficacy in several EGFR-mutant non-small cell lung cancer (NSCLC) cell lines and xenograft models, including in vivo tumor regression in the H1975 model, which harbors EGFR L858R/T790M. In in vivo models, EGF816 also demonstrated a pharmacokinetic (PK)-tumor pharmacodynamic (PD) relationship, with PD outlasting PK, consistent with the irreversible binding of EGF816 to EGFR. Dose-dependent anti-tumor efficacy was observed in several xenograft models, and EGF816 was well tolerated with no body weight loss observed at efficacious doses.

In preclinical toxicology studies conducted in rats and dogs, EGF816 was overall well tolerated at plasma concentrations that resulted in anti-tumor activity in rodent efficacy models. One of the off-targets of EGF816 is Tyrosine kinase expressed in hepatocellular carcinoma (TEC) family kinases. The results of a T-cell Dependent Antigen Response (TDAR) assay in rats indicated a trend for a dose-response effect of EGF816 on inhibiting the generation of antigen-specific antibodies to a foreign antigen; this effect was reversible following withdrawal of EGF816. In the first-in-human study of EGF816 in patients with EGFR-T790M NSCLC, preliminary PK data demonstrated that the EGF816 exposure increased largely in proportion to dose 75 mg to 350 mg, quaque die/ daily (q.d.) and the terminal half-life (T1/2) ranged from 13 hours (h) to 18h EGF816 appears to be efficacious at doses of 75 mg q.d. and above, and preliminary exposure-response analyses showed a flat relationship between EGF816 steady state trough concentration and overall response rate (RR). Preliminary population PK analysis indicated similar exposures from the matched doses in capsule and tablet formulations.

